5.4.3.3 Abortions

Any abortion should be classified as a serious adverse event (as the Sponsor considers abortions to be medically significant), recorded on the Adverse Event eCRF, and reported to the Sponsor immediately (i.e., no more than 24 hours after learning of the event; see Section 5.4.2).

5.4.3.4 Congenital Anomalies/Birth Defects

Any congenital anomaly/birth defect in a child born to a female patient exposed to study drug or the female partner of a male patient exposed to study drug should be classified as a serious adverse event, recorded on the Adverse Event eCRF, and reported to the Sponsor immediately (i.e., no more than 24 hours after learning of the event; see Section 5.4.2).

5.5 FOLLOW-UP OF PATIENTS AFTER ADVERSE EVENTS

5.5.1 Investigator Follow-Up

The investigator should follow each adverse event until the event has resolved to baseline grade or better, the event is assessed as stable by the investigator, the patient is lost to follow-up, or the patient withdraws consent. Every effort should be made to follow all serious adverse events considered to be related to study drug or trial-related procedures until a final outcome can be reported.

During the study period, resolution of adverse events (with dates) should be documented on the Adverse Event eCRF and in the patient's medical record to facilitate source data verification.

All pregnancies reported during the study should be followed until pregnancy outcome.

5.5.2 Sponsor Follow-Up

For serious adverse events, adverse events of special interest, and pregnancies, the Sponsor or a designee may follow up by telephone, fax, electronic mail, and/or a monitoring visit to obtain additional case details and outcome information (e.g., from hospital discharge summaries, consultant reports, autopsy reports) in order to perform an independent medical assessment of the reported case.

5.6 POST-STUDY ADVERSE EVENTS

After the end of the reporting period for serious adverse events and adverse events of special interest (defined as 90 days after the last dose of study drug or initiation of a new anti-cancer treatment whichever comes first), all deaths, regardless of cause, should be reported through use of the Long-Term Survival Follow-Up eCRF. In addition, if the investigator becomes aware of a serious adverse event that is believed to be related to prior study drug treatment, the event should be reported through use of the Adverse Event eCRF.

5.7 EXPEDITED REPORTING TO HEALTH AUTHORITIES, INVESTIGATORS, INSTITUTIONAL REVIEW BOARDS, AND ETHICS COMMITTEES

The Sponsor will promptly evaluate all serious adverse events and adverse events of special interest against cumulative product experience to identify and expeditiously communicate possible new safety findings to investigators, IRBs, ECs, and applicable health authorities based on applicable legislation.

To determine reporting requirements for single adverse event cases, the Sponsor will assess the expectedness of these events using the following reference documents:

- Cobimetinib Investigator's Brochure
- Atezolizumab Investigator's Brochure
- *Summary of Product Characteristics (SPC) for regorafenib (Stivarga® SPC 2017)*

The Sponsor will compare the severity of each event and the cumulative event frequency reported for the study with the severity and frequency reported in the applicable reference document.

Reporting requirements will also be based on the investigator's assessment of causality and seriousness, with allowance for upgrading by the Sponsor as needed.

6. STATISTICAL CONSIDERATIONS AND ANALYSIS PLAN

This is a randomized, Phase III, global, multicenter, open-label study designed to evaluate the safety and efficacy of cobimetinib plus atezolizumab and atezolizumab monotherapy as compared to treatment with regorafenib in approximately 360 patients with unresectable locally advanced or metastatic colorectal adenocarcinoma.

The efficacy analyses of OS, PFS, and ORR will be performed on all randomized patients (i.e., intent to treat [ITT]) irrespective of whether the assigned treatment was actually received. DOR will be assessed in patients who have an objective response. For all efficacy analyses, patients will be grouped according to the treatment assigned at randomization.

The safety population will include all randomized patients who received any amount of study drug. Patients who are randomized into the study but do not receive any amount of study drug will not be included in the safety population. For safety analyses, patients will be grouped according to whether any amount of cobimetinib and/or atezolizumab was received, including the case when study drug (cobimetinib and/or atezolizumab) was received in error.

Statistical details for all the analyses will be documented in the Statistical Analysis Plan.

6.1 DETERMINATION OF SAMPLE SIZE

The study will randomize approximately 360 patients, including a minimum of 180 patients with extended RAS-mutant mCRC (assuming a prevalence of at least 50%), to cobimetinib plus atezolizumab (Arm A), atezolizumab monotherapy (Arm B), and regorafenib (Arm C) with the randomization ratio of 2:1:1, respectively.

The type 1 error (α) for the analysis of the primary endpoint of OS in the comparison of cobimetinib plus atezolizumab (Arm A) against the control arm of regorafenib (Arm C) is 0.05 (2-sided). If OS in the comparison of Arm A against Arm C is statistically significant, then the OS in the comparison of Arm B against Arm C will be tested at a 2-sided α level of 0.05.

The sample size of this study is determined on the basis of the number of events required to demonstrate efficacy with regard to OS in both comparisons (Arm A vs. Arm C and Arm B vs. Arm C).

The overview of the Type I error (α) control is shown in [Figure 3](#).

Figure 3 Overview of Hierarchical Testing Sequence for Type I Error^a Control (2-Sided)

OS=overall survival.

^a OS will be tested at a 2-sided significance level $\alpha=0.05$ only if the result of previous testing is positive (i.e., statistically significant).

The estimate of the number of events required to demonstrate efficacy with regard to OS is based on the following assumptions:

- Two-sided significance level of 0.05
- Arm A versus Arm C: 87% power to detect an HR of 0.61, corresponding to an improvement in median OS from 6.4 months in Arm C to 10.5 months in Arm A
- Arm B versus Arm C: 80% power to detect an HR of 0.61, corresponding to an improvement in median OS from 6.4 months in Arm C to 10.5 months in Arm B
- No interim analysis for OS
- Dropout rate of 10% in 24 months
- Hierarchical testing of Arm A versus Arm C followed by Arm B versus Arm C to control the overall α level of 5%

With these assumptions, approximately 360 patients in total will be randomized into this study, with approximately 270 patients for the comparison of Arm A versus Arm C and approximately 180 patients for the comparison of Arm B versus Arm C. *The OS final analysis will be conducted when there are approximately 235 deaths in the study. This is expected to occur approximately 23 months after the first patient is randomized. At that time, it is expected that approximately 178 deaths for the comparison of Arm A versus Arm C and approximately 127 deaths for the comparison of Arm B versus Arm C will have occurred.*

This number of events corresponds to a minimum detectable difference in HR of approximately 0.73 for the Arm A versus Arm C comparison and approximately 0.71 for the Arm B versus Arm C comparison.

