Official Title: A Phase III, Open-Label, Multicenter, Three-Arm, Randomized Study to Investigate the Efficacy and Safety of Cobimetinib Plus Atezolizumab and Atezolizumab Monotherapy vs. Regorafenib in Patients With Previously Treated Unresectable Locally Advanced or Metastatic Colorectal Adenocarcinoma

NCT Number: NCT02788279

Document Date: SAP Version 2: 27-Nov-2017

STATISTICAL ANALYSIS PLAN

TITLE: A PHASE III, OPEN-LABEL, MULTICENTER, THREE-ARM, RANDOMIZED STUDY TO INVESTIGATE THE EFFICACY AND SAFETY OF COBIMETINIB PLUS ATEZOLIZUMAB AND ATEZOLIZUMAB MONOTHERAPY VS. REGORAFENIB IN PATIENTS WITH PREVIOUSLY TREATED UNRESECTABLE LOCALLY ADVANCED OR METASTATIC COLORECTAL ADENOCARCINOMA

PROTOCOL NUMBER: GO30182

STUDY DRUG: Cobimetinib; atezolizumab

VERSION NUMBER: 2

IND NUMBER: 130,091

EUDRACT NUMBER: 2016-000202-11

SPONSOR: F. Hoffmann-La Roche Ltd

PLAN PREPARED BY: [REDACTED], Ph.D

DATE FINAL: 02 March 2017

DATE AMENDED: Version 2: See electronic date stamp below

STATISTICAL ANALYSIS PLAN APPROVAL

Name	Reason for Signing	Date and Time (UTC)
[REDACTED]	Company Signatory	27-Nov-2017 21:56:09

CONFIDENTIAL

This is an F. Hoffmann-La Roche Ltd document that contains confidential information. Nothing herein is to be disclosed without written consent from F. Hoffmann-La Roche Ltd.

STATISTICAL ANALYSIS PLAN AMENDMENT RATIONALE for Version 2

The Statistical Analysis Plan (SAP) has been amended mainly due to the change in the order of hierarchical testing for efficacy endpoints, overall survival (OS), progression-free survival (PFS) and objective response rate (ORR).

GO30182 was designed and powered to evaluate the primary endpoint, OS in two comparisons: Arm A (cobimetinib plus atezolizumab) versus Arm C (regorafenib), and Arm B (atezolizumab) versus Arm C.

However, the original procedure to control type 1 error proposed in the SAP Version 1 (v1) consisted of OS as well as two secondary endpoints, PFS and ORR, in the hierarchical testing order of: OS, PFS and ORR in the comparison of Arm A vs. Arm C, followed by OS, PFS and ORR in the comparison of Arm B vs. Arm C.

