2.4 ANALYSIS TIMING

2.4.1 Primary Analysis Timing

No interim analyses are planned for the efficacy endpoints. The OS final analysis for the primary comparisons of Arm A versus Arm C and Arm B versus Arm C will be conducted when there are a total of approximately 235 OS events from the study, which is expected to occur approximately 23 months after the first patient is randomized, based on the study assumptions and the projected accrual rate. The number of events, the event ratio, the minimum detectable difference (MDD), and the power for each comparison are summarized in [Table 1](#).

Table 1 Analysis for Overall Survival for Primary Comparisons (Arm A vs. Arm C and Arm B vs. Arm C)

	OS Final Analysis	
	Arm A vs. Arm C	Arm B vs. Arm C
Events (event ratio)	178 (66%)	127 (71%)
MDD in HR	0.73	0.71
Power	87%	80%

FPI=first patient in; HR=hazard ratio; MDD=minimum detectable difference; OS=overall survival; event ratio=number of events / number of patients randomized.

Note: OS final analysis to occur approximately 23 months from FPI.

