2.4.2 Analysis Timing for Experimental Arm Comparison

If both of the primary comparisons (i.e., Arm A vs. Arm C and Arm B vs. Arm C) are statistically significant for OS, then OS between the experimental arms (i.e., Arm A vs. Arm B) will be compared at the time of the primary analysis. At this time, a total of approximately 165 OS events are expected from Arms A and B, corresponding to an

MDD in HR of 0.72. The operating characteristics for selected target HRs comparing Arm A with Arm B is presented in [Table 2](#).

Table 2 Operating Characteristics for the Comparison of Arm A versus Arm B with Approximately 165 Overall Survival Events

Target HR	Power	95% CI ^a
0.61	85%	(0.44, 0.84)
0.67	69%	(0.48, 0.93)
0.75	42%	(0.54, 1.04)

FPI= first patient in; HR = hazard ratio; mOS = median overall survival.

^a 95% CI when the target HR is observed.

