4.4.4 Evaluation of Each Drug's Contribution to The Combination

If both of the primary comparisons (i.e., Arm A vs. Arm C and Arm B vs. Arm C) for OS are statistically significant, OS as well as other secondary and exploratory endpoints will be compared between experimental arms (i.e., Arm A vs. Arm B) using the same methods described in Sections 4.4.1, 4.4.2, and 4.4.3. The clinical benefit associated with adding cobimetinib to atezolizumab will be evaluated with the focus on clinically meaningful improvement rather than statistical significance.

If the OS comparison for Arm A versus Arm C is statistically significant but the OS comparison for Arm B versus Arm C is not, atezolizumab's contribution to the treatment effect in Arm A will be evaluated for all study endpoints. The evaluation of clinical benefit by adding atezolizumab to the combination will use descriptive statistics (e.g., point estimate and confidence intervals) without hypothesis testing.

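### The 80% power stated for Arm B versus Arm C ignores the gate on Arm A versus Arm C; under the planned sequence it is about 74%

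*Protocol*

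**What the plan says.** Protocol Section 6.1 lists the sample-size assumptions. For the second primary comparison it states "Arm B versus Arm C: 80% power to detect an HR of 0.61". The matching figure for Arm A versus Arm C is 87%, also at HR 0.61. The same list includes "Hierarchical testing of Arm A versus Arm C followed by Arm B versus Arm C". The gate is set out earlier in the section, in the sentence that begins "If OS in the comparison of Arm A against Arm C is statistically significant, then the OS in the comparison of Arm B"; the second test then uses the full two-sided 0.05. The section bases the sample size on the "number of events required to demonstrate efficacy with regard to OS in both comparisons".

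The 80% also appears in the Protocol synopsis, in SAP Section 2.3 and in SAP Table 1. SAP Section 2.4.1 introduces that table by saying that "the minimum detectable difference (MDD), and the power for each comparison are summarized". The SAP's rationale for Version 2 says that "GO30182 was designed and powered to evaluate the primary endpoint, OS in two comparisons". None of these places calls the 80% marginal, and none gives a joint power or a power under the hierarchy.

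**The concern.** In a fixed sequence, the procedure can reject the second hypothesis only if it also rejects the first. The chance of establishing Arm B is therefore the chance that both tests are significant. That is below the power of the Arm B test alone unless the first test is certain to succeed or never fails when the second would succeed. With a first-step power of 87%, some loss is expected.

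The Protocol treats Arm B versus Arm C as a primary objective. A reader who sees the hierarchy listed beside the 80%, and a sample size said to cover both comparisons, can reasonably take 80% as the chance that the trial as planned establishes Arm B. The same joint event also opens a later step: SAP Section 4.4.4 compares Arm A with Arm B "If both of the primary comparisons (i.e., Arm A vs. Arm C and Arm B vs. Arm C) for OS are statistically significant", and SAP Section 2.4.2 sets the same condition. The planning probability of reaching that comparison is therefore also not given.

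The point concerns the planning figure only. Type I error control, and the reading of any result that is actually tested, are unaffected.

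**Working it through.** **Inputs** (Protocol 6.1; SAP 2.3 and 2.4): two-sided alpha 0.05, no interim analysis of OS, HR 0.61 in both comparisons (medians 6.4 and 10.5 months), allocation 2:1:1, 178 deaths for A versus C, 127 for B versus C, 235 in total.

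**1. Reproduce the stated powers.** For one log-rank test, power = Φ(|ln HR| × √(d·p·(1−p)) − 1.96), where d is the number of deaths, p is the allocation fraction and |ln 0.61| = 0.4943.
- A versus C: √(178 × 2/9) = 6.289; × 0.4943 = 3.109; Φ(1.149) = 87.5% (stated 87%).
- B versus C: √(127 × 1/4) = 5.635; × 0.4943 = 2.785; Φ(0.825) = 79.5% (stated 80%).

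Both stated figures are therefore single-test powers with no allowance for the gate.

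**2. Implied deaths per arm.** C = 178 + 127 − 235 = 70; A = 178 − 70 = 108; B = 127 − 70 = 57. As a check, A + B = 165, which agrees with SAP 2.4.2: "a total of approximately 165 OS events are expected from Arms A and B".

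**3. Correlation of the two statistics through Arm C.** The documents do not state it, but it can be derived in two ways.
- From allocation: √(2/3 × 1/2) = 0.577.
- From implied deaths: (1/70) / √[(1/108 + 1/70)(1/57 + 1/70)] = 0.522.

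**4. Probability that both tests are significant.** This is P(Z_A > 1.96 and Z_B > 1.96) for a bivariate normal pair with the means above. For the implied-deaths rows the means are 0.4943/√(1/108 + 1/70) = 3.221 and 0.4943/√(1/57 + 1/70) = 2.771.

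| Variance basis | A alone | B alone | Correlation | Both | Lost to gate (points) |
|---|---|---|---|---|---|
| Allocation | 87.5% | 79.5% | 0.522 | 73.4% | 6.1 |
| Allocation | 87.5% | 79.5% | 0.577 | 74.0% | 5.6 |
| Implied deaths | 89.6% | 79.1% | 0.522 | 74.4% | 4.7 |
| Implied deaths | 89.6% | 79.1% | 0.577 | 74.9% | 4.3 |
| Stated 87% and 80% | 87% | 80% | 0.522 to 0.577 | 73.5% to 74.1% | 6.5 to 5.9 |

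The result is not sensitive to the correlation. With the stated powers, values from 0.5 to 0.7 give 73.3% to 75.4%. Independent tests would give 0.87 × 0.80 = 69.6%, and only perfect correlation would give 80%.

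**5. Simulation check.** Three-arm trials were simulated with exponential survival, 360 patients at 2:1:1, 10% dropout in 24 months, a cut at the 235th death and an unstratified log-rank test, using 20,000 trials per setting. The documents do not give an accrual period, so uniform accrual over 8 to 18 months was assumed; 14 months puts the cut at 22.5 months, against 23 planned. Power for B alone was 78.4% to 79.1%. Both tests were significant in 74.1% to 75.0% of trials, so the gate cost 4.0 to 4.4 points. The correlation was 0.57 to 0.58, and the Monte Carlo standard error was about 0.3 points.

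**6. Dependence on Arm A.** With a true HR of 0.67 for A versus C and B kept at 0.61, the probability of declaring Arm B superior is 62.4% to 63.2% (allocation), 64.4% to 65.1% (implied deaths) and 63.9% to 64.4% (simulation; accrual of 10, 14 and 18 months).

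**The case against.** The strongest reply is that nothing stated is false. The 80% is right for the single test, SAP Table 1 is introduced as giving power for each comparison, and its columns tie 127 deaths, a minimum detectable HR of 0.71 and 80% to B versus C alone. The hierarchy bullet gives control of alpha as its purpose and says nothing about power. The gate is stated openly, and reporting power test by test is common. Once the gate has opened, power for B versus C is 83% to 85%, so 80% does not overstate the test when it is performed. Finally, the gate itself costs 4 to 6 points, so it does not explain the whole difference between 80% and 74% under every method.

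Much of this stands. The 80% is not a calculation error, the per-test reading is plausible, and the cost of the gate should be quoted as 4 to 6 points. The HR of 0.67 for Arm A is a what-if and not a planning assumption. The simulation rests on assumed accrual and an unstratified test, whereas the primary test is stratified.

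The reply does not supply the missing number. The documents say that the events were chosen to demonstrate efficacy in both comparisons under a listed hierarchy, and no figure describes what that procedure achieves for Arm B. The conditional power answers a different question, because it leaves out the trials in which the gate never opens.

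**Conclusion.** The concern holds. The 80% is the marginal power of Arm B versus Arm C. Under the planned fixed sequence, with HR 0.61 in both comparisons, the probability of declaring Arm B superior is about 74% (73% to 75% across methods). The gate accounts for 4 to 6 points, and any remaining difference from 80% comes from rounding and approximation.

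The conclusion rests on proportional hazards at the planned effects, the planned death counts, and a correlation of about 0.52 to 0.58 derived from the shared control arm. This is a planning and disclosure matter that should be corrected. It gives no reason to change the design.

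**What to change.** In Protocol Section 6.1, the Protocol synopsis and SAP Section 2.3, and in a footnote to SAP Table 1, label the 80% as the marginal power of Arm B versus Arm C (127 deaths, HR 0.61). Then add a sentence such as:

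> Under the hierarchical procedure, with HR 0.61 in both comparisons, the probability of declaring Arm B superior is about 74%, allowing for the correlation from the shared control arm (about 0.52 to 0.58).

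The cost is wording only, plus a stated figure about 6 points less favourable.

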6.2 SUMMARIES OF CONDUCT OF STUDY

Enrollment, study drug administration, and discontinuation from the study will be summarized by treatment arm. The incidence of study drug discontinuation for reasons other than disease progression will similarly be tabulated. Protocol violations, including

major violations of inclusion/exclusion criteria, will be summarized in a similar manner by treatment arm.

6.3 SUMMARIES OF TREATMENT GROUP COMPARABILITY

Demographic characteristics, such as age, sex, race/ethnicity, and baseline disease characteristics will be summarized by treatment arms for the ITT populations. Descriptive statistics (mean, median, standard deviation, and range) will be presented for continuous data, and frequencies and percentages will be presented for categorical data. Study treatment administration will be summarized by treatment arm for all treated patients.

6.4 EFFICACY ANALYSES

Unless otherwise noted, all efficacy analyses will include all randomized patients (ITT analysis), and patients will be grouped according to the treatment assigned at randomization.

6.4.1 Primary Efficacy Endpoint

The primary efficacy endpoint is OS, which is defined as the time (in months) between the date of randomization and the date of death due to any cause. Patients who have not died at the time of analysis will be censored at the date when they were last known to be alive.

Comparisons with respect to OS between two treatment arms (i.e., Arm A vs. Arm C, Arm B vs. Arm C) will be tested based on a stratified log-rank test. The stratification factors will be extended RAS mutation status of the tumor and time since diagnosis of first metastasis (< 18 months and \geq 18 months).

Each comparison will be tested at a 2-sided significance level of 0.05 within the ITT population:

- Test to reject the null hypothesis of no difference in OS between either experimental arm (i.e., Arm A or Arm B) and the control arm (Arm C) in the ITT population. If the 2-sided p-value corresponding to the stratified log-rank test is less than 0.05, the null hypothesis will be rejected.

The HR for OS will be estimated using a stratified Cox model. Two-sided 95% CIs for the HR will be provided. The stratified analyses will incorporate extended RAS mutation status and time since diagnosis of first metastasis as stratification factors. Results from an unstratified log-rank test and the unstratified HR will also be presented. Kaplan-Meier methodology will be used to estimate median OS for each treatment arm, and the Kaplan-Meier curves will be provided. The Brookmeyer-Crowley methodology will be used to construct the 95% CI for the median OS for each treatment arm ([Brookmeyer and Crowley 1982](#)).

The comparison between the two experimental arms (Arm A vs. Arm B) will be conducted for descriptive purposes.

6.4.2 Secondary Efficacy Endpoints

The secondary endpoints include investigator-assessed PFS, ORR, and DOR per RECIST v1.1. The analyses of PFS, ORR, and DOR will take place at the time of the OS analysis.

PFS is defined as the time between date of randomization and the date of first documented disease progression or death, whichever occurs first. Disease progression will be determined based on investigator assessment using RECIST v1.1. Data from patients who have not experienced disease progression or death will be censored at the last tumor assessment date and known to be free of disease progression. Data from patients with no post-baseline tumor assessment will be censored at the randomization date plus 1 day. Comparisons with respect to PFS between the two treatment arms will be tested based on a 2-sided stratified log-rank test. The HR for PFS will be estimated using a stratified Cox model. Two-sided 95% CIs for the HR will be provided. Stratified analyses will incorporate the same stratification factors as for the analysis of OS.

Results from an unstratified log-rank test and the unstratified HR will also be presented. Kaplan-Meier methodology will be used to estimate median PFS for each treatment arm, and the Kaplan-Meier curves will be provided.

ORR is defined as the proportion of patients who had a confirmed objective response of CR or PR assessed by the investigator according to the RECIST v1.1. An estimate of ORR and its 95% CI will be calculated using the Clopper-Pearson method for each treatment arm.

Treatment difference in ORR will be tested using the stratified Cochrane-Mantel-Haenszel test, stratified by the same factors used in the OS analysis, and a 95% Hauck-Anderson CI will be calculated for the difference in ORR between treatment arms.

DOR is defined as the period measured from the date of the first occurrence of a CR or PR (whichever status is recorded first) until the first date that progressive disease or death is documented. Disease progression will be determined on the basis of investigator assessment with use of RECIST v1.1. DOR will be assessed in patients who have an objective response during the study as determined by the investigator with use of RECIST v1.1. Patients who have not progressed and who have not died by the date of data cutoff for analysis will be censored at the time of last tumor assessment date. If no tumor assessments were performed after the date of the first occurrence of a CR or PR, DOR will be censored at the date of the first occurrence of a CR or PR plus 1 day. Median DOR will be estimated using the Kaplan-Meier method, and the 95% CI will be calculated using the method of Brookmeyer and Crowley (1982). DOR analysis is

performed on the basis of a non-randomized subset of patients (i.e., patients who achieve an objective response); therefore, formal hypothesis testing will not be performed for this endpoint.

